1. LIST OF ABBREVIATIONS

AE	Adverse Event
СРА	Cyproterone Acetate
CRF	Case Report Form
dl	Decilitre
DHT	Dihydroxytestosterone
DRE	Digital Rectal Examination
ETV	Early Termination Visit
FSH	Follicle Stimulating Hormone
GCP	Good Clinical Practice
GMP	Good Manufacturing Practices
GnRH	Gonadotrophin Releasing Hormone
ICH	International Conference on Harmonisation
IM	Intra-Muscular
IMP	Investigational Medicinal Product
ITT	Intention To Treat
LH	Luteinising Hormone
LHRH	Luteinising Hormone Releasing Hormone
LHRHa	Luteinising Hormone Releasing Hormone Analogue
MCV	Mean Cell Volume
mg	Milligram
MHRA	Medicines and Healthcare products Regulatory Agency
ng	Nanogram
PP	Per Protocol
PSA	Prostate Specific Antigen
REC	Research Ethics Committee
SAE	Serious Adverse Event
SC	Subcutaneous
SPC	Summary of Product Characteristics
SR	Sustained Release
STT	Serum Total Testosterone
STTCL	Serum Total Testosterone Castration Level
SUSAR	Suspected Unexpected Serious Adverse Reaction

TEAE	Treatment Emergent Adverse Event
TNM	Tumor-Nodes-Metastasis (Staging System)
UHB	University Hospitals Bristol NHS Foundation Trust
WBC	White Blood Cell
Week	A week is defined as 7 days, i.e. Week 1 would equal Day 7, and Week 4 would equal Day 28.

2. BACKGROUND INFORMATION

2.1 Disease Review

Prostate cancer is a malignant tumour of the prostate gland. In most developed and developing countries, prostate cancer is the most commonly diagnosed malignancy affecting men beyond middle age, and is second only to lung cancer as a cause of cancer deaths in men⁽¹⁾.

The general prognosis remains poor with 70% survival at 10 years compared to the general population. About half of the cases are diagnosed at a locally advanced stage whilst about 30% present with bone metastases at the time of diagnosis ⁽¹⁾.

Worldwide, there has been a consistent increase in the incidence of clinically significant disease in recent years. Moreover, because prostate cancer is primarily a disease affecting men over the age of 50 years, the worldwide trend towards an ageing population means the number of prostate cancer deaths is predicted to increase markedly during the next two decades.

Despite the high incidence of prostate cancer, relatively little is known about the fundamental causes of the disease. A number of risk factors have been established; age, race, diet, environmental factors, family history and hormone levels, all seem to have an influence over the development of cancer.

Testosterone and its more potent metabolite dihydroxytestosterone (DHT) are essential for normal prostate growth, and thus may play a part in the development of prostate cancer. Prostate cancer almost never develops in men castrated before puberty, or in individuals deficient in 5α reductase (the enzyme that converts testosterone to DHT). Although there is no correlation between circulating androgen concentrations and the risk of prostate cancer, a raised 5α reductase level may be associated with a higher incidence of the disease. At present the precise role of androgens and oestrogens in the development of prostate cancer remains to be established.

Most patients, in whom prostate cancer is suspected, are identified on the basis of abnormal findings on digital rectal examination (DRE) or, more commonly, by raised prostate specific antigen (PSA) levels. PSA is a glycoprotein responsible for liquefying semen. Approximately 20% of men with PSA levels above the normal range (\geq 4ng/dL) have prostate cancer, and the risk increases to more than 60% in men with PSA levels above 10ng/dL. These markers are very useful as, in general, the earlier prostate cancer is detected, the better the outlook for the patient.

Men with locally advanced or metastatic prostate cancer can present with a combination of symptoms:

- symptoms of bladder outflow obstruction such as frequency, hesitancy and poor flow,
- symptoms resulting from local extension of the tumour, such as haematuria or pain due to hydronephrosis secondary to obstruction of the ureters,
- symptoms resulting from distant metastases, such as low back pain, spinal cord compression, bone pain anaemia or weight loss.

There is a broad wealth of available treatment strategies for prostate cancer patients. The various treatments involve surgery and prostatic radiotherapy as

well as systemic treatments such as bisphosphonates and radionuclides in case of bone lesions, and hormonal treatments ⁽²⁾.

More recently, cytotoxic chemotherapy with a docetaxel-based regimen has been reported to significantly improve median survival of metastatic hormone refractory prostate cancer patients ⁽³⁾.

Under normal physiological conditions, the hypothalamus stimulates the pulsatile release of Luteinising Hormone Releasing Hormone (LHRH). This targets receptors on the anterior pituitary gland to stimulate both the synthesis and pulsatile release of the gonadotrophins; Luteinising Hormone (LH) and Follicle Stimulating Hormone (FSH). LH attaches to receptors on the Leydig cells of the testes promoting testosterone production, which is thought to play an essential role in prostate growth. It is thought therefore, that if testosterone levels are suppressed, the prostate gland growth may also be impeded, which would help in patients with abnormally growing prostate glands.

The hormone dependent nature of prostate cancer has formed the pathophysiological rationale for the hormone therapy of prostatic carcinoma and the introduction of LHRH analogues (LHRHa's) into the therapeutic armamentarium has revolutionised the treatment of advanced prostate cancer ⁽⁴⁾.

LHRHa (also known as Gonadotrophin Releasing Hormone analogues (GnRHa) work by mimicking the physiological actions of LHRH. The analogues have a much longer half life than naturally occurring LHRH. This results in a down-regulation of receptors in the pituitary, an inhibition of FSH/LH production and a significant decrease in testosterone production, after a transitory phase of hyper-stimulation; in effect inducing medical castration.

Medical castration, by administration of LHRHa, reduces the intraprostatic concentration of DHT by over 80%; which is comparable to surgical orchidectomy (surgical removal of the testes; castration). This has huge advantages both physically and psychologically to the patients.

Achieving and maintaining serum testosterone at castration levels are the main goal of therapy with LHRHa⁽⁵⁾. Typically the serum total testosterone castration level (STTCL) is set at 50 ng/dL. Whilst there is some suggestion that the lower the serum total testosterone level, the better, this suggestion is still the subject of debate and lower castrate levels are not widely used as a treatment target in the UK.

2.3 Clinical Trial Rationale

In the UK, Decapeptyl SR is marketed as a palliative treatment for patients with advanced prostate cancer. Both the 3mg and 11.25 mg formulations are licensed in the UK for administration by IM injection.

If Decapeptyl SR is as effective when given by subcutaneous injection as when given by intramuscular injection then this would offer patients a greater choice of injection sites and facilitate ease of patient self injection.

There is limited data available on the administration of triptorelin by sub-cutaneous (SC) injection, however, studies performed to date, have demonstrated that triptorelin is as effective safe and well tolerated when injected by SC injection as it is when given by IM injection in patients with prostate cancer. (Klippel *et al.*⁷)

An ongoing pharmacokinetic study to evaluate 2 different 4-Month formulations of Decapeptyl includes a study arm (12 patients) in which patients receive Decapeptyl SR 15 mg, (as triptorelin acetate) injected by the SC route. Preliminary results demonstrate that the proportion of responders and the time taken to achieve STTCL is similar to results obtained in previous studies evaluating administration of triptorelin acetate via the IM route (data on file, Ipsen).

There are other similar Sustained Release (or Depot) LHRHa available in the UK that are licensed for both SC and IM injection. These include leuprorelin acetate (Prostap[®] SR, Wyeth) and another brand of triptorelin acetate (Gonapeptyl Depot).

The purpose of this study therefore is to evaluate the efficacy, safety and tolerability of Decapeptyl SR when administered by subcutaneous (SC) injection in order to provide greater patient choice in method and site of injection. In accordance with usual treatment practice in the UK, the main objectives of this study are to achieve and maintain STTCL. For the purpose of this study STTCL is defined as a serum total testosterone level of ≤ 50 ng/dL

2.4 Primary Objective

To evaluate the efficacy of Decapeptyl SR when given by SC injection in patients with prostate cancer. This will be determined by evaluating the proportion of patients who achieve STTCL 4 months after the first injection.

2.5 Secondary Objectives

To evaluate the efficacy of an initial injection with Decapeptyl SR 3mg when given by SC injection. This will be determined by evaluating the proportion of patients who achieve STTCL 1 month after the first injection.

To evaluate the efficacy of a repeat injection with Decapeptyl SR 11.25mg when given by SC injection. This will be determined by evaluating the proportion of patients who achieve STTCL 1 month after the second injection.

To assess changes in plasma triptorelin levels after administration of Decapeptyl SR by SC injection at all assessment time-points in comparison to Baseline.

To assess changes in the levels of Serum Total Testosterone (STT) and Prostate Specific Antigen (PSA), after administration of Decapeptyl® SR by SC route injection at all assessment time-points in comparison to the Screening visit.

3. STUDY DESIGN

3.1 Study Design

This is an, Open-Label, Single-Arm study.

3.2 Study Population

Approximately 50 patients with prostate cancer who satisfy the inclusion / exclusion criteria will be recruited into the study from routine clinics and within secondary care referrals.

3.3 Study Duration

Up to 1 month after Screening, eligible patients will return for the Baseline visit and will receive 4 months treatment with Decapeptyl SR.

Each patient's participation in the trial will last up to 5 months (including Screening period).

3.4 Study Schedule

Table 2Study Schedule

a) Assessment	Visit 1 - Screening	Visit 2 - Baseline	Visit 2a (phone)	Visit 3	Visit 3a (phone)	Visit 4	Visit 5 /ETV
Month (visits calculated using calendar months)	≤ 1 mth before D0	DAY 0	V2 + 1 Day	M1 (+ 3 days)	V3 + 1 Day	M2 (+ 3 days)	M4 (+ 3 days)
Written Informed Consent	\checkmark						
Review Inc/ Exc Criteria	✓	✓					
Record Demographics	✓						
Record Medical History (inc. prostate cancer)	~						
Digital Rectal Examination	\checkmark^1						
Physical Examination	✓						✓
Vital Signs	✓	✓		 ✓ 		✓	✓
Blood Samples (serum total T, PSA) ²	✓	✓		 ✓ 		✓	✓
Blood samples (haematology & biochemistry)	√			✓ (LFTs only)			~
Blood sample for plasma triptorelin		 ✓ 		 ✓ 		✓	✓
Dipstick Urinalysis	✓						✓
Start 2wks tx with Anti-Androgen (CPA)		 ✓ 					
Decapeptyl SR injection ³		✓ (3mg)		✓ (11.25mg)			
Injection tolerability assessment		V	✓ (24hrs after injection)	V	✓ (24hrs after injection)		
Concomitant Medications	\checkmark	✓	V	✓	V	✓	✓
Adverse Events		✓	✓	✓	✓	✓	✓
End of Study Record							✓

3.5 Study Visits

3.5.1 Visit 1 - Screening (within 4 weeks prior to Baseline) – For ALL Patients

Potential study patients will be identified from clinics at the study site and either approached during routine clinic appointments, or in writing about the study.

¹ If the patient has had a DRE within 4 weeks of the Screening visit, this does not need to be repeated.

² Blood samples are to be collected between 09:00 and 11:00hrs.

³ Decapeptyl SR injections to be administered after all study procedures have been completed.

Referrals may be sought from within secondary care. Local patient support groups may be made aware of the study as applicable.

Suitable patients will be invited to attend the clinic for a Screening visit between 2 days and 4 weeks prior to the Baseline visit. Written informed consent will be obtained prior to any study related assessments or procedures being performed. The visit will take place between 09:00 and 11:00 hours as the blood samples must be collected within this time-frame (due to the possibility of diurnal variations in testosterone levels). The following assessments and procedures will be completed at this visit:

- Patient's eligibility for the study will be checked by reviewing the inclusion and exclusion criteria.
- Demographic details (date of birth, ethnic origin, height, weight).
- Relevant medical and surgical history, including current medical conditions. This will include their history of prostate cancer, TNM staging, Gleason score and PSA.
- Physical examination findings (including digital rectal examination (DRE) if this has not been done within 4 weeks prior to this visit).
- Vital signs (height, weight, blood pressure and pulse rate). Blood pressure and heart rate should be recorded sitting, after the patient has been seated at rest for 5 minutes.
- Blood samples (for analysis of serum total testosterone (STT), PSA, haematology and biochemistry). These samples should be collected between 09:00 and 11:00 hours.
- Urine sample (for dipstick urinalysis). In the even of any significant findings on urinalysis, further investigations should be performed at the discretion of the Investigator.
- Prior and concomitant medications.
- An appointment will be made for eligible patients to return to the clinic for the Baseline visit up to 1 month later.

3.5.2 Baseline (Week 0)

Eligible patients will return to the clinic within the following month for the Baseline visit. At the Baseline visit:

- Patients' eligibility for the study will be re-checked.
- Blood samples will be collected for analysis of STT, PSA and plasma triptorelin prior to dosing.
- Any adverse events or changes in concomitant medications since the Screening visit will be recorded.

Patients who are still considered to be eligible for the study after completion of all Baseline assessments will then receive a SC injection of Decapeptyl SR 3 mg. Subcutaneous injections should be administered into the anterior abdominal wall. Details of any immediate injection site reaction(s) will be recorded.

To minimise risk of tumour flare, all patients will start adjuvant therapy with an anti-androgen, cyproterone acetate (CPA). Each patient will take 100 mg CPA, three times a day, for 2 weeks starting on the day of the Baseline visit.

24 hours after the injection, the site will call the patient to check whether there have been any tolerability issues following the injection. Details will be recorded in the patients CRF. Patients will provide feedback on:

- Pain (severity, time of onset in relation to the injection, duration).
- Redness (severity, time of onset in relation to the injection, duration).
- Swelling (severity, time of onset in relation to the injection, duration).
- Severity of injection site reactions will be graded using a 4 point scale (none, mild, moderate and severe).

3.5.3 Visit 3 (month 1)

One month after the Baseline visit (+/- 3 days), patients will be required to attend the clinic for a follow up visit and their second injection. (Visit 3). At this visit the following will occur:

- Blood samples will be collected for analysis of STT, PSA, plasma triptorelin and liver function tests (LFTs).
- Any new or altered adverse events or concomitant medications will be recorded.

Patients will then receive a SC injection of Decapeptyl SR 11.25 mg. Subcutaneous injections should be administered into the anterior abdominal wall. Details of any immediate injection site reaction(s) will be recorded.

24 hours after the injection, the site will call the patient to check whether there have been any tolerability issues following the injection. Details will be recorded in the patients CRF.

3.5.4 Visit 4 (month 2)

Patients will return to the clinic for visit 4 (day 84) Visits can be +/- 3 days.

At each study visit any adverse events or changes in concomitant medications since the previous visit will be recorded. At all visits, blood samples will be taken for analysis of levels of STT, PSA, and plasma triptorelin.

3.5.5 Visit 5 (day 112:) Study Completion / Early Termination Visit

Patients will return to the clinic 4 months after the Baseline visit for the study completion visit. If a patient discontinues from the study prematurely, every effort should be made to perform an early termination visit, including the assessments listed here.

- Vital signs
- Urinalysis
- Blood samples for STT, PSA, plasma triptorelin, haematology and biochemistry
- Concomitant Medication and adverse events

At the patient's last study visit details of their completion of the study / withdrawal from the study will be recorded. At the end of the study patients will

receive the standard medical care for their prostate cancer. This may involve treatment with Decapeptyl SR or another marketed LHRHa at the discretion of the treating physician.

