	1. To evaluate the efficacy of an initial treatment with Decapeptyl SR 3 mg when given by SC injection. This will be determined by evaluating the proportion of patients who achieve STTCL 1 month after the first injection.
	2. To evaluate the efficacy of a repeat treatment with Decapeptyl SR 11.25 mg when given by SC injection. This will be determined by evaluating the proportion of patients who achieve STTCL 1 month after the second injection.
	3. To assess the changes in plasma triptorelin levels after administration of Decapeptyl SR by SC injection at all assessment time-points in comparison to Baseline.
	4. To assess changes in the levels of Serum Total Testosterone (STT) and Prostate Specific Antigen (PSA), after administration of Decapeptyl SR via the SC route at all assessment time-points in comparison to Baseline.
	Safety & Tolerability Objectives:
	1. To assess the safety of Decapeptyl SR when administered by SC injection.
	 To assess the tolerability of Decapeptyl SR when administered by SC injection.
Study Design:	This is an open-label, single-arm trial designed to assess the efficacy, safety and tolerability of Decapeptyl SR when administered by SC injection. Enrolled patients will be those who have a diagnosis of prostate cancer and for whom medical castration by means of LHRHa

is indicated. Each patient's participation in the trial will last up 5 months (including Screening period).
During the study, patients will receive one injection of Decapeptyl SR 3 mg (the 1-month sustained release formulation) and one injection of Decapeptyl SR 11.25 mg (the 3-month sustained-release formulation). The 3 mg injection will be administered at the study visit 2, on Day 0 (Baseline) and the 11.25 mg injection will be administered one month later, at visit 3. Patients will have additional follow-up visits at Month 2 and Month 4 (End of Study Visit).
All visit dates will be calculated based on calendar months in order to ensure consistency with the recommended injection schedule for Decapeptyl SR.
Written informed consent will be obtained from all patients prior to any study related procedures or assessments being performed.
All study visits will begin between 09:00 and 11:00 hours as blood samples must be collected during this time window (due to possible diurnal variations in testosterone levels)
Potential patients will be invited to attend a Screening visit (visit 1) for the study. At the Screening visit the following will be collected:

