	24 hours after the injection, the site will call the patient to check whether there have been any tolerability issues following the injection. Details will be recorded in the patients CRF.
	Patients will return to the clinic for a follow up assessment 2 months after the Baseline visit (visit 4). At this visit any new or altered adverse events or concomitant medications will be recorded. Blood samples will be collected (for analysis of levels of STT, PSA and plasma triptorelin).
	Four months after the Baseline visit, patients will return for an End of Study Visit (Visit 5) a physical examination will be performed and vital signs (weight, blood pressure, pulse rate) will be recorded. Blood samples will be collected (for analysis of levels of STT, PSA, plasma triptorelin, haematology and biochemistry). A dipstick urinalysis will be performed. Details of any new or altered adverse events or concomitant medications will be recorded.
	At the end of their study participation, patients will receive the standard medical care for their prostate cancer. This may involve treatment with Decapeptyl SR or any other marketed LHRHa at the discretion of the treating physician.
Study Population:	Approximately 50 patients will be enrolled in order to achieve 42 evaluable patients at the end of the study.
	Patients must satisfy the following eligibility criteria:
	Inclusion Criteria
	Patients must fulfil all of the following criteria in order to be included in the study:

1.	The patient has given written (personally signed and dated) informed consent before starting any study-related procedure, which means any assessment or evaluation that would not have formed part of their normal medical care.
2.	The patient is male and is 18 years of age or older.
3.	The patient has a histologically or cytologically confirmed diagnosis of prostate cancer and meets the following criteria:
	 Stage T3 or T4, N (any), M (any) (see Appendix 1) with a PSA >5ng/ml or
	 Biochemical relapse following radical prostatectomy or radical radiotherapy for prostate cancer
4.	Medical castration by means of LHRHa therapy is indicated for the patient.
5.	The patient has a life expectancy of at least 12 months.
6.	The patient is able and willing to comply with the requirements of the protocol.
Ex	clusion Criteria
	tients who fulfil any of the following criteria, will not be included in e study:
1.	The patient has undergone bilateral orchidectomy.

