6.1.1 Serum Total Testosterone

Venous blood samples will be collected for analysis of serum total testosterone by direct venous puncture at Baseline and Week 4.

Due to the possibility of diurnal variation of serum testosterone levels, blood samples to assess testosterone level should be drawn in the morning between 9:00 and 11:00hrs. Blood samples will be collected into an SST or PST tube and transferred to the lab at ambient temperature.

6.1.2 Prostate Specific Antigen (PSA),

Venous blood samples will be collected for analysis of PSA at all study visits. Blood samples will be collected into an SST or PST tube and transferred to the lab at ambient temperature.

6.1.3 Plasma Triptorelin,

Blood samples will be collected for analysis of plasma triptorelin levels at all study visits from screen onwards.

Blood samples will be collected into 5 ml Vacutainer tubes (containing EDTA and aprotinin), and will be centrifuged at 4°C at 2000 g for 15 minutes. The plasma will be rapidly transferred to two polystyrene tubes. The tubes will be stoppered (airtight) and stored at -20°C. Samples will be transferred in batches to Ipsen Pharma S.A and will be analysed by Ipsen Pharma S.A.

The analytical method that will be used to determine triptorelin in plasma samples is based on a radioimmunoassay (RIA) procedure, previously validated in the experimental conditions used at Ipsen Pharma $S.A^{(8)}$. The limit of quantification of the assay is 0.010 ng/ml.

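### The day labels for Visits 4 and 5 (day 84, day 112) and the testosterone sampling list in section 6.1.1 contradict the calendar-month schedule on which the endpoints rest; day 84 would not measure the secondary endpoint it serves

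*Protocol*

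**What the plan says.** **Endpoints.** The primary objective (section 2.4) is timed from the first injection: "This will be determined by evaluating the proportion of patients who achieve STTCL 4 months after the first injection". One secondary objective (section 2.5) is timed from the second: "This will be determined by evaluating the proportion of patients who achieve STTCL 1 month after the second injection". The second injection is given at Visit 3, one month after Baseline, so this secondary endpoint belongs to the Month 2 visit.

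**Scheduling rule.** The synopsis states that "All visit dates will be calculated based on calendar months". Table 2 (section 3.4) repeats the rule in its time row, "Month (visits calculated using calendar months", and gives Visits 3, 4 and 5 as M1, M2 and M4, each with a 3-day tolerance. For Visit 4 the synopsis says: "Patients will return to the clinic for a follow up assessment 2 months after the Baseline visit (visit 4".

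**Text that departs from it.**
- Section 3.5.4 is headed month 2, but its first sentence reads: "Patients will return to the clinic for visit 4 (day 84) Visits can be +/- 3 days".
- Section 3.5.5 is headed "Visit 5 (day 112:) Study Completion / Early Termination Visit", and the table of contents repeats that label. The body of the section places the visit 4 months after Baseline.
- Section 6.1.1 reads: "Venous blood samples will be collected for analysis of serum total testosterone by direct venous puncture at Baseline and Week 4". It names no other sampling time.

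**The concern.** These are instructions that a site works from when it books visits and draws blood, and a sample taken on the wrong day cannot be retaken. A site that books Visit 4 from section 3.5.4 collects its testosterone sample at a time that does not correspond to the secondary endpoint. A site that books Visit 5 from the heading of 3.5.5 takes the primary-endpoint sample outside the protocol's own window.

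Section 6.1.1 is the section devoted to the primary variable, yet it omits the Month 4 sample on which the primary test depends, as well as the Screening and Month 2 samples. The neighbouring sections on PSA and plasma triptorelin refer to all study visits, so the shorter testosterone list can be read as deliberate.

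**Working it through.** **Inputs.** Calendar-month rule and 3-day windows: synopsis and Table 2. Second injection at Month 1: section 3.5.3 and Table 2. Day 84: section 3.5.4. Day 112: heading of section 3.5.5. A week is 7 days and Week 4 is day 28: list of abbreviations.

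**Where the day labels come from.** 84 = 3 × 28 and 112 = 4 × 28. Day 112 is therefore month 4 on a 28-day count. Day 84 is month 3 on that count, and month 2 would be 2 × 28 = day 56. So day 84 does not fit a month 2 visit under either convention.

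**Length of calendar months**, over all 1,461 baseline dates in a four-year cycle:
- 1 month: 28 to 31 days
- 2 months: 59 to 62 days (for example, 1 January to 1 March in a non-leap year is 31 + 28 = 59)
- 4 months: 120 to 123 days (for example, 1 July to 1 November is 31 + 31 + 30 + 31 = 123)

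**Comparison, counted from Baseline.**

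| Visit | Calendar-month day | With ±3 days | Day label | With ±3 days | Difference |
|---|---|---|---|---|---|
| 4 | 59–62 | 56–65 | 84 | 81–87 | 84 − 62 = 22 to 84 − 59 = 25 days late |
| 5 | 120–123 | 117–126 | 112 | 109–115 | 120 − 112 = 8 to 123 − 112 = 11 days early |

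For neither visit do the two windows overlap on any of the 1,461 baseline dates.

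**Comparison, counted from a second injection given exactly at Month 1.**
- Visit 4: Month 2 is 28 to 31 days after the injection. Day 84 is 84 − 31 = 53 to 84 − 28 = 56 days after it.
- Visit 5: Month 4 is 89 to 92 days after the injection. Day 112 is 112 − 31 = 81 to 112 − 28 = 84 days after it.

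**Allowing both windows to move** (injection and sample each up to 3 days, so 6 in total):
- Visit 4: Table 2 permits 28 − 6 = 22 to 31 + 6 = 37 days. The day-84 text permits 53 − 6 = 47 to 56 + 6 = 62. These still do not meet.
- Visit 5: Table 2 permits 89 − 6 = 83 to 92 + 6 = 98 days. Day 112 permits 81 − 6 = 75 to 84 + 6 = 90. These overlap.

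**Sampling list.** Week 4 is day 28, which is 0 to 3 days before Month 1, so the first-month endpoint stays inside its window. Against section 6.1.1 stand:
- Table 2, with testosterone at Screening, Baseline and Visits 3, 4 and 5;
- the synopsis, for Visits 4 and 5;
- section 3.5.4, which calls for testosterone at all visits;
- section 3.5.5, which lists it among the Visit 5 and early-termination samples.

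**Sample size.** The single-stage design (42 patients, cut-off 39) is not affected. The exact binomial calculation gives a one-sided alpha of 0.0208 and a power of 0.843, which agree with the stated 2% and 84%.

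**The case against.** The best defence is that the protocol settles most of this itself. The calendar-month rule is express and appears twice. Day 112 stands only in a heading and its contents entry, and the sentence beneath gives 4 months. Section 6.1.1 does not say that its two times are the only ones, and four other places require testosterone at the later visits. A careful site would probably collect the Month 4 sample at the right time.

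Much of this stands, and it limits two stronger readings.

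- A reader might infer from 6.1.1 that no primary endpoint would be collected. That would require a site to disregard Table 2, the synopsis and both visit sections. The documents support an incomplete and contradictory list and nothing beyond that.
- A reader might infer that sampling at day 112 misses late testosterone escape and so tilts the result towards success. The documents give no figure for such escape. Table 2's own windows already allow a sample 83 days after the second injection, which lies within the 81 to 84 days implied by day 112. The appended product information for the 11.25 mg formulation reports castration at day 84 in 98% of patients and stable triptorelin until day 90. Those data are for the intramuscular route and do not settle subcutaneous behaviour, but they do not support a presumed escape either.

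The defence does not reach day 84. That label is in body text, has its own tolerance, and fits no reading of month 2.

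**Conclusion.** The contradiction is real and should be fixed. The firmest part is Visit 4: day 84 is 22 to 25 days late and 53 to 56 days after the second injection, where the secondary endpoint calls for 28 to 31. No use of the 3-day windows closes that gap. For Visit 5, the day-112 label is 8 to 11 days early and outside the Month 4 window, and it conflicts with its own section's body. Section 6.1.1 is incomplete against the rest of the protocol.

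The day counts assume that Baseline is day 0 and, for the intervals after the second injection, that this injection is given at Month 1 unless the windows are stated. The intended design is clear from the synopsis and Table 2, so this is an inconsistency in site instructions. The design itself is not at fault. Neither loss of the primary endpoint nor a bias of known direction is shown.

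**What to change.** Reconcile sections 3.5.4, 3.5.5 and 6.1.1 and the table of contents with the synopsis, sections 2.4 and 2.5, and Table 2:

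- In 3.5.4, replace day 84 with Month 2 (calendar months, ±3 days).
- In the heading of 3.5.5 and its contents entry, replace day 112 with Month 4 (calendar months, ±3 days).
- In 6.1.1, list serum total testosterone at Screening, Baseline, Month 1, Month 2 and Month 4 or early termination.

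The cost is a wording amendment. No visit or sample is added beyond Table 2, and the sample size and cut-off stay as they are. No new rule on how out-of-window samples count in the analysis is needed to resolve this conflict.
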